Calculations of sample size were based on the primary endpoint of WOMAC-PF at 3 months. We propose to recruit a total of 240 subjects (96 in each exercise arm and 48 in the usual care group) to allow approximately 86 subjects in each exercise arm and 43 in the usual care group available for a complete case analysis at 3 months (assuming 10% attrition at 3 months). We propose a larger number of subjects in both exercises groups (outpatient rehabilitative exercise and community-based group exercise) because we expect a moderate effect size between these two interventions; whereas we propose a smaller number of subjects in the usual care group because we expect a large effect size between the usual medical care group and either of the exercise groups. Thus, with an alpha level of 0.05, 2 tails test, a sample size of 172 (n=86 in each exercise group) will provide 81% power to detect a difference as small as 3.3-point difference between the two exercise groups in WOMAC-PF (SD of 7.7 from our pilot work).¹¹ This would correspond to a difference in less than 2 activities (out of the 17 queried in the WOMAC-PF) having improved from “about moderate difficulty” to “no difficulty”. The sample size of 43 in the usual medical care group will provide 80% power to detect a difference of 5.2-point difference in WOMAC-PF between the usual medical care group and any exercise group. Power analysis was conducted in NCSS/PASS. Moreover, this sample size will provide adequate power (above 80%) to test the hypothesis related to the secondary outcomes (performance-based physical function and physical activity). For example, we will be able to detect differences between the two exercise groups as small as 0.7 sec in the stair climbing test, 0.4 in the chair-rise test, 0.02 m/sec in walking speed, 1.4 sec in the single leg stance, and 35 min/day in light intensity physical activity (based on SD of our own preliminary data). The differences we will be able to detect between the usual care and any intervention groups are as small as 1.01 sec in the stair climbing test, 0.54 in the chair-rise test, 0.03 m/sec in walking speed, 1.6 sec in the

PRINCIPAL INVESTIGATOR (LAST, FIRST, MIDDLE): [name]

single leg stance, and 49 min/day in light intensity physical activity. These differences are smaller than the known minimal detectable changes for these outcomes.⁸⁸⁻⁹⁰

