For Aim 2, we plan to assess predictors of response based on a minimum change score of 20% in BOTH the WOMAC-PF and the composite score of functional performance at 3 months, thus yielding a binary outcome. For this aim, we will have a combination of those initially randomized to one of the exercise arms and those in the usual care group who were later randomized to the exercise arms for a total of approximately 200. If the expected response rate ranges between 50% and 60%, we would be able to detect an odds ratio of 2.2 to 2.4 with 80% power assuming a binary predictor with 50% split in the sample. In addition, with approximately 100 responders, we will be able to accommodate 9 predictors in the multiple logistic regression based on rule of thumb guidelines for sample size in logistic regression (min of response/nonresponse/ (#predictors+1) \geq 10).

Data Analysis

[name] will oversee data analyses. We will evaluate the statistical properties of baseline and follow-up outcome measures, including potential outliers, normality and missing data. Measures of central tendency (means, medians, other percentiles) and dispersion (standard deviations, ranges) will be computed for continuous variables, whereas frequency distributions will be calculated for categorical data. Distributions of baseline characteristics will be compared between groups to assess effectiveness of randomization, and statistical or clinical differences will be adjusted in the analyses. Data transformations may be applied if needed and guided by clinical meaningfulness.

Hypothesis 1.1 - Subjects in Groups 1 and 2 will demonstrate better physical function as compared to Group 3.

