Hypothesis 2- A group of baseline biomedical and psychosocial measures will associate with treatment response.

Each subject will be classified as a responder or non-responder based on a minimum change score of 20% in BOTH the WOMAC-PF and the composite score of functional performance at 3 months, thus yielding a binary outcome. Baseline variables will be summarized separately for responders and non-responders. Unadjusted odds ratios will be estimated using univariate logistic regression. To consolidate potential predictors, we will test for collinearity among baseline variables that are associated with response. Baseline measures associated with response at the $p<0.15$ level in unadjusted models will be added to multivariable logistic regression models to assess predictors of treatment response. We will limit the number of predictors going into any one model to no more than one predictor per 10 responses (or 10 non-responses, whichever is less); if more variables are significant, the model will be limited to the most significant variables, after adjusting for those deemed a-priori to be clinically significant. We expect different predictors for each group. For example, patients with worse physical function and impairments (e.g., limited range of motion and muscle weakness) will do better with individual outpatient exercise whereas those with heightened psychosocial factors (e.g., anxiety and depressive symptoms) will respond better to group exercise in the community.^{48,70-72}

Exploratory Hypothesis- Adherence and co-interventions will be similar in all groups. The attrition rate and adverse events- mainly number of falls- will be lower in Groups 1 and 2 compared to Group 3.

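### Aim 2 models improvement among exercise exposures only, with no arm or predictor-by-arm term, so what it calls predictors of treatment response may be prognostic factors

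*Combined protocol and SAP*

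**What the plan says.** The Aim 2 paragraph under Sample Size defines the analysis set as "a combination of those initially randomized to one of the exercise arms and those in the usual care group who were later randomized", the second allocation being to clinic or community exercise, and puts its size at about 200. Every record in that set is therefore a period of exercise.

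The outcome is binary: a "minimum change score of 20% in BOTH the WOMAC-PF and the composite score of functional performance at 3 months". Hypothesis 2, under Data Analysis, is that "A group of baseline biomedical and psychosocial measures will associate with treatment response". The method is univariate logistic regression, a p < 0.15 screen, and then a multivariable logistic model with a cap on the number of predictors. That section names no arm term, no predictor-by-arm term and no untreated comparator. It does say that different predictors are expected for each group. The Psychosocial Measures and Knee Impairments items under Potential Predictors of Treatment Response also hypothesize opposite predictors for clinic and community exercise.

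Two other places bear on the point. The Design Overview describes the aim as finding predictors of functional recovery, and has all groups assessed at baseline, 3 months and 6 months. The Usual medical care section gives, as one reason for the wait-list design, that this group's data can enter the Aim 2 analysis.

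**The concern.** Within-patient change during exercise has at least two components: the effect of exercise, and whatever would have happened anyway (continuing recovery, regression to the mean). Patients enter 2 to 4 months after surgery, when some further recovery without exercise is plausible. They need a WOMAC-PF of only 9 points to be eligible. At that score a 20% change is 0.20 x 9 = 1.8 points, against an SD of 7.7. The composite must also change by 20%, but nothing in the definition isolates the exercise effect.

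A baseline factor that raises the chance of improvement equally with and without exercise will be associated with response in an exercise-only sample. Called a predictor of treatment response, it could be used to steer patients towards or away from exercise when it carries no information about who gains from it. The Design Overview asks about comparative effectiveness given patients' personal characteristics, with usual care among the options, so the distinction matters to the trial's own question.

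**Working it through.** **Inputs from the documents.** Aim 2 N of about 200; response rate 50% to 60%; a binary predictor with a 50% split; 3-month completers 86 / 86 / 43; WOMAC-PF SD 7.7; attrition 10% at 3 months and 15% at 6 months. Two-sided alpha 0.05 is stated for the primary endpoint ("with an alpha level of 0.05, 2 tails test") and assumed here for Aim 2, which states none. **Input not in the documents:** the usual-care response rate, taken as 20% to 50%.

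**1. The plan's figure.** It claims to "detect an odds ratio of 2.2 to 2.4 with 80% power", "assuming a binary predictor with 50% split in the sample". Compare 100 v 100 patients:

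power = Φ{ [ |p2 − p1| − 1.96 √(2 p̄(1−p̄)/100) ] / √([p1(1−p1) + p2(1−p2)]/100) }

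Solving for 80% power gives OR 2.22 (50% as overall rate), 2.26 (50% as the rate at the reference level), 2.26 (60% overall) and 2.39 (60% reference). The stated range reproduces. The sample size also fits: 192 x 0.90 = 173, plus 48 x 0.85 = 41 (or 37 after a further 10% loss), gives 210 to 214 exercise exposures.

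**2. A purely prognostic factor.** Suppose the OR is the same with and without exercise, so the ratio of odds ratios is 1. The exercise-only analysis cannot see that, and its chance of significance is the power in step 1. For OR 2.2 and overall rate 50%: p1 = 0.403, p2 = 0.597; (0.1946 − 0.1386)/0.0694 = 0.807; Φ(0.807) = 79.0%.

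| Overall response | OR | p < 0.05 | passes p < 0.15 screen |
|---|---|---|---|
| 50% | 2.2 | 79.0% | 91.0% |
| 50% | 2.4 | 86.7% | 95.0% |
| 60% | 2.2 | 77.2% | 89.9% |
| 60% | 2.4 | 85.1% | 94.2% |

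If the quoted rates are instead read as reference-level rates, the p < 0.05 column runs from 72% to 85%.

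**3. Exercise v usual care, responder scale.** With 172 v 43 and a 50/50 factor there are 86 and 21.5 patients per cell. Set the usual-care OR to 1 and let R be the ratio of odds ratios:

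SE² = Σ 1/(n p q) over the four cells; power = Φ(ln R / SE − 1.96)

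- R = 2.2, exercise 50%, usual care 50%: SE² = 0.097 + 0.372, SE = 0.685, ln 2.2 / 0.685 = 1.15, power 21%.
- The same with usual care 20%: SE² = 0.097 + 0.581, SE = 0.823, power 16%.
- Over all combinations, power is 16% to 21% for R = 2.2 and 18% to 25% for R = 2.4.
- For 80% power, ln R = 2.80 x SE. This gives R = exp(2.80 x 0.699) = 7.1 at best (exercise 50%, usual care 50%) and exp(2.80 x 0.852) = 10.9 at worst (exercise 60%, usual care 20%).

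**4. Exercise v usual care, continuous WOMAC-PF** (no gain from covariates): 2.80 x 7.7 x 2 x √(1/172 + 1/43) = 2.80 x 7.7 x 2 x 0.1705 = 7.4 points.

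**5. Clinic v community interaction.** With 86 to 100 per arm, the formula in step 3 gives 28% to 33% power at R = 2.4 and a detectable R of about 5.2 to 6.4. On continuous WOMAC-PF with 86 v 86: 2.80 x 7.7 x 2 x √(2/86) = 6.6 points.

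**The case against.** *The aim is prognostic.* The Design Overview's wording supports this, and response is openly defined as within-patient change. But Potential Predictors of Treatment Response, the Aim 2 paragraph and Hypothesis 2 all speak of response. The mixed wording is a reason to correct the label. It does not make the treatment-response reading safe.

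*Usual-care data are already in Aim 2.* A reader might infer that these patients are wasted. They are not: they serve Aim 1 and enter Aim 2 after crossover. Only their control-period data lack a stated role. The remark in the Usual medical care section fits the post-crossover use set out under Sample Size. Even if control-period data were pooled, without a predictor-by-arm term they would not separate response from recovery.

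*The main hypotheses concern clinic versus community exercise.* This largely stands. A reader might infer that comparing the two exercise arms cannot help because both contain the same recovery. The opposite is true: under randomization, shared recovery cancels in a predictor-by-arm contrast, and that contrast tests the hypotheses the plan states. But the plan does not specify it, and it could not show who benefits from exercise over usual care.

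*Interactions will be too imprecise.* The low power is real, and 7.4 points exceeds the 5.2-point difference from usual care on which the trial is sized. That argues for estimates with intervals rather than a significance rule. It does not justify giving a prognostic model a treatment-response label.

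**Conclusion.** The point holds as a gap between the Aim 2 analysis and its label. As written, Aim 2 can identify who improves during exercise. It does not distinguish that from who improves because of exercise.

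The 77% to 87% applies to one 50/50 factor with an OR of 2.2 to 2.4, N = 200, and 50% to 60% taken as the overall response rate. It is not the probability of surviving the full screen-and-select procedure, which was not computed.

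The mislabelling matters only if patients also improve without exercise. A reader might infer that natural recovery is large, but the documents give no usual-care response rate, so its size is unknown. Nor does the design make the separation impossible: the control-period data are to be collected, and only the analysis is missing. The plan's detectable odds ratio is not in error, and the primary WOMAC-PF analysis is unaffected.

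**What to change.** 1. Keep the pooled exercise-only model, but label it *predictors of improvement during exercise* and describe it as prognostic.
2. Add predictor-by-arm interactions over months 0-3 in the originally randomized arms, for exercise v usual care and for clinic v community. Prefer continuous WOMAC-PF adjusted for baseline.
3. Fit one predictor, or a few prespecified predictors, at a time. The plan allows 9 terms with about 100 responders. Three arms need 2 arm terms plus 3 terms per predictor (a main effect and two interactions), so one model holds only (9 − 2)/3, or about two, predictors.
4. Report the interactions as exploratory estimates with confidence intervals, and base any statement about differential treatment response on them.

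The cost is analysis time and modest claims; no new data are needed. The interaction analysis leaves out the roughly 37 to 41 post-crossover exercise exposures, which stay in the pooled model. The intervals will be wide, so many of these estimates are likely to be inconclusive, and the report should say so in advance.

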Potential Predictors of Treatment Response- Variables at the baseline that we believe may be potential predictors of treatment response, in addition to physical function (described above) include:

- Demographics and Biomedical Characteristics such as age, gender, race, education, BMI, self-rated health (excellent, good, fair, poor, or bad), discharge placement, number of prior rehabilitation sessions, TKR technique, and surgeon experience will be collected.
- Medication prescribed and over-the-counter used for pain will be recorded in the medication form. We will record the current and highest dosage of any pain medication used during the last month.
- Comorbidity data will be gathered using the Cumulative Illness Rating Scale.⁶⁹ Subjects will be asked to indicate conditions with which they have been formally diagnosed by a physician in the past.
- Psychosocial Measures will include factors that our and other groups have demonstrated to be associated with physical function in knee OA and include:^{48,70-72} 1) Fear; 2) Anxiety; 3) Self-Efficacy; 4) Depression; 5) Coping. We hypothesize that patients with higher fear, anxiety, depression and catastrophizing coping along with low self-efficacy who participated in the community-based group exercise classes will be able to improve physical function, whereas the ones who participated in the individual outpatient exercise will not. Fear-avoidance beliefs will be measured by the Tampa Scale for Kinesiophobia.⁷³ Anxiety will be measured using the Beck Anxiety Index.⁷⁴ Self-efficacy will be measured by the Arthritis Self Efficacy Scale.⁷⁵ Depression will be assessed by the Center for Epidemiologic Studies Short Depression Scale.⁷⁶ Coping will be measured by the Coping Strategy Questionnaire.^{77,78}

PRINCIPAL INVESTIGATOR (LAST, FIRST, MIDDLE): [name]

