- **Knee Impairments** – We hypothesize that patients with increased knee pain, decreased knee range of motion, and lower extremity muscle strength who participated in the outpatient rehabilitation will be able to improve physical function whereas the ones who participated in the community-based group exercise classes will not. Knee pain in the surgical and non-surgical knee will also be measured using an 11-point pain scale. Knee range of motion will be measured by a standard goniometer. We will measure the strength of the muscle groups that have been related to the outcome of TKR^{45,79} including knee extension strength and hip abduction strength measured using an isokinetic dynamometer (Biodex System 4 Pro, Shirley, NY) as we described before.⁴⁵

Capturing Potential Harm of Interventions- Growing evidence suggests that regular physical activity does not have deleterious effects on the survival of the prosthesis.^{80,81} The exercises we propose are not expected to cause any harm because they exert relatively low forces over the prosthesis.⁸²⁻⁸⁵ Regardless of the anticipated safety of the exercises, we will ascertain that interventions offer no harm by closely monitoring adverse events:

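### The Aim 2 power (80% at an odds ratio of 2.2 to 2.4) holds for predictors common to both exercise arms; the arm-specific hypotheses have no power figure and no analysis that tests them

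*Combined protocol and SAP*

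**What the plan says.** The Aim 2 paragraph of the Sample Size section combines patients first randomized to exercise with "those in the usual care group who were later randomized to the exercise arms for a total of approximately 200". For a response rate of 50% to 60%, it states that "we would be able to detect an odds ratio of 2.2 to 2.4 with 80% power assuming a binary predictor with 50% split". It then allows nine predictors, from about 100 responders in the combined sample.

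Hypothesis 2, under Data Analysis, is worded generally: a set of baseline measures is associated with treatment response. The steps are univariate logistic regression, a screen at p<0.15, then multivariable logistic regression. No treatment-arm term, predictor-by-arm term or arm-stratified model is named. The same section adds "We expect different predictors for each group".

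The section on potential predictors of treatment response is more specific:
- Psychosocial measures: patients with worse scores who attend community classes "will be able to improve physical function, whereas the ones who participated in the individual outpatient exercise will not".
- Knee impairments: patients with worse impairments improve with outpatient rehabilitation, "whereas the ones who participated in the community-based group exercise classes will not".

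**The concern.** The power statement concerns one odds ratio estimated from everyone who exercised. The two hypotheses on psychosocial measures and knee impairments say that a predictor matters differently in the two arms. Such a claim rests either on about 100 patients within one arm or on the contrast between the two arms' odds ratios. Both are less precise than the pooled estimate.

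The screen adds a separate problem. If it is run on the pooled sample, a predictor that acts in one arm is diluted, and one that acts in opposite directions is averaged away before any multivariable model is fitted.

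At stake is which patients do better in which programme. A reader who takes 80% as the power for that question would give a negative result more weight than it can bear.

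**Working it through.** **Inputs.** From the Sample Size section: about 200 patients, 50-60% response, binary predictor with a 50% split, 80% power. Two-sided 0.05 is stated for the primary endpoint ("with an alpha level of 0.05, 2 tails test") and assumed to carry over to Aim 2. About 100 patients per exercise arm is also assumed: the allocation is "96 in each exercise arm and 48 in the usual care group", and the ratio for re-randomizing usual care is not given. The response rate is read two ways, as the overall rate or as the rate in the reference group of the predictor.

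**1. The plan's own figure.** With n patients per predictor level, response rates p0 and p1, and their mean p̄:

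power = Φ{[(p1 − p0)√n − 1.96√(2p̄(1 − p̄))] / √(p0(1 − p0) + p1(1 − p1))}

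- Overall response 50%, OR 2.2: p0 = 0.403, p1 = 0.597, n = 100. Power = Φ[(1.946 − 1.386)/0.694] = Φ(0.81) = 79%. The OR for 80% power is 2.22.
- Reference rate 60%, OR 2.4: p0 = 0.600, p1 = 0.783. Power is 80.3%. The OR for 80% power is 2.39.

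The stated 2.2-2.4 therefore reproduces, as a pooled test of one common effect.

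**2. Within one arm (n = 50 per level).** Same formula. At 50% overall and OR 2.2: Φ[(1.376 − 1.386)/0.694] = Φ(−0.01) = 49%.

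**3. Predictor-by-arm interaction, with the stated OR in one arm and 1 in the other.** Wald test with SE = √Σ 1/[50p(1 − p)] over four cells of 50. At 50% overall and OR 2.2, the acting arm contributes 2 × 1/(50 × 0.403 × 0.597) = 0.166 and the other arm 2 × 1/(50 × 0.25) = 0.160. SE = √0.326 = 0.571, ln 2.2 = 0.788, and power = Φ(0.788/0.571 − 1.96) = Φ(−0.58) = 28%.

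**4. Interaction with opposite effects (OR in one arm, 1/OR in the other).** The contrast doubles to 2 × 0.788 = 1.577 and SE = √(4 × 0.0832) = 0.577. Power = Φ(1.577/0.577 − 1.96) = Φ(0.77) = 78%.

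Power at OR 2.2 / OR 2.4:

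| Response rate | Pooled | Within one arm | Interaction, one arm only | Interaction, opposite |
|---|---|---|---|---|
| 50% overall | 79 / 87% | 49 / 58% | 28 / 33% | 78 / 86% |
| 60% overall | 77 / 85% | 48 / 56% | 27 / 32% | 76 / 84% |
| 50% reference | 77 / 85% | 48 / 56% | 28 / 33% | 76 / 84% |
| 60% reference | 72 / 80% | 44 / 51% | 26 / 30% | 75 / 82% |

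For 80% power, the within-arm test needs OR 3.1-3.7. The interaction needs a ratio of odds ratios of about 5.0-5.5 on the overall reading. On the reference reading, a one-arm effect needs 5.9-7.5. With 215 patients instead of 200, the ranges are 46-61% within an arm and 27-35% for the one-arm interaction.

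**5. The p<0.15 screen on the pooled sample (simulation, OR 2.4, 50-60% overall response).** A predictor acting in both arms passes about 94% of the time, and one acting in a single arm about 52%. With opposite effects at 50% response, predictor-positive patients average (0.608 + 0.392)/2 = 0.50, as do predictor-negative patients. The pooled OR is then 1, and the predictor passes about 13% of the time, close to the 15% of a null predictor.

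**The case against.** The strongest reply is that nothing has been miscalculated. The Aim 2 paragraph states its conditions openly, Hypothesis 2 is general, and the stated power fits it. This stands. A reader might infer that the sample-size arithmetic is wrong, or that Aim 2 as a whole is underpowered. The documents support neither.

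A second reply is that the hypotheses on psychosocial measures and knee impairments describe a strong contrast, with improvement in one arm and none in the other, and attach no odds ratio to it. Applying 2.2-2.4 to them is an assumption of this check. They could also be read as comparing arms within a type of patient, and on function rather than on the binary responder outcome. This stands in part. The true contrast may be larger, and with opposite effects interaction power is near or above 80%, so arm-specific effects are not beyond the trial's reach. But the plan names no interaction test, and a pooled screen would discard most opposite-effect predictors.

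Third, the analysis text does not say outright that the screen is pooled. It refers to models in the plural and expects predictors to differ by group, so separate models by arm are a possible reading. Against this, the nine-predictor allowance is computed from the pooled sample. If by-arm models were meant, the cancellation disappears, but power is then the 44-58% of a single arm. With 40-50 patients in the smaller outcome class, the plan's own rule allows three or four predictors per model (40/10 − 1 = 3; 50/10 − 1 = 4).

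That a negative Aim 2 would in fact be over-read is a prediction that the documents cannot settle.

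**Conclusion.** The concern holds as a gap between the stated power and the arm-specific hypotheses. It is not an arithmetic error. The 80% at OR 2.2-2.4 is right for predictors common to both arms. For the arm-specific hypotheses, two figures should be kept apart because they belong to different tests: about 44-58% within one arm, and about 26-33% for an interaction when the predictor acts in one arm only. The opposite-effects case is different in kind: the interaction test would have about 75-86% power, but the plan names no such test and its screen, read as pooled, would usually remove the predictor.

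These sizes rest on about 100 patients per arm, a 50% split, 50-60% response, two-sided 0.05, and carrying the plan's odds ratios over to the arm-specific question. Aim 2 did not set the sample size; WOMAC-PF at 3 months did. This is a cheap improvement.

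**What to change.** In the Aim 2 paragraph of the Sample Size section, say that OR 2.2-2.4 applies to predictors with the same effect in both exercise arms. Add the detectable ratio of odds ratios for a predictor-by-arm interaction (about 5 or more for 80% power), with its assumptions.

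In the Hypothesis 2 analysis:
- Keep the pooled p<0.15 screen for common predictors, and say that it is pooled.
- For the psychosocial and knee-impairment predictors already named in the plan, fit models with arm, predictor and predictor-by-arm terms whatever the pooled screen shows.
- Report the interaction estimates with confidence intervals, and label these analyses exploratory.

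Do not replace the pooled screen with separate p<0.15 screens by arm. Those do not test whether effects differ. In simulation, a predictor acting equally in both arms (OR 2.2-2.4) passes in exactly one arm about 37-44% of the time and would look arm-specific.

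The cost is a few extra models and a less favourable stated figure for the arm-specific question. No extra patients are needed.
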